**8.1.6 Interim Analysis**

No interim analysis is planned for this study.

**8.2 Determination of Sample Size**

This study should have a 30 month recruitment period where it is anticipated that approximately 200 subjects will be recruited. With this sample size the proportion of responders, defined as the proportion of subjects with a highly or completely satisfied response after 16 weeks of ADA + MTX therapy, based on an Investigator assessment and subject self-assessment, can be estimated within  $\pm 4.9\%$  with 95% confidence when the point estimate is 15%, within  $\pm 6.4\%$  with 95% confidence when the point estimate is 30%, or within  $\pm 6.9\%$  with 95% confidence when the point estimate is 50%. Additional accuracy estimates are provided in the Table below.

**Table 4: Accuracy Estimates with a Sample Size of 200 Subjects**

Estimated Proportion of Responders	Accuracy Estimate
5%	3.0%
10%	4.2%
15%	4.9%
20%	5.5%
25%	6.0%
30%	6.4%
35%	6.6%
40%	6.8%
45%	6.9%
50%	6.9%

**Note: Proportion of responders can be estimated with +/- accuracy with 95% confidence. The size of the 95% Confidence Interval would be 2×Accuracy**

Due to the recent enrollment plan change (enroll 50 patients or as the number of enrollment by 31-Dec-2016), Updated accuracy estimates with a sample size of 50 subjects, about the proportion of subjects with a highly or completely satisfied response after 16 weeks of ADA + MTX therapy based on an Investigator assessment and subject self-assessment, are provided in the table below.

**Table 5: Accuracy Estimates with a Sample Size of 50 Subjects**

Estimated Proportion of Responders	Accuracy Estimate
5%	6.0%
10%	8.3%
15%	9.9%
20%	11.1%
25%	12.0%
30%	12.7%
35%	13.2%
40%	13.6%
45%	13.8%
50%	13.9%

**Note:** Proportion of responders can be estimated with +/- accuracy with 95% confidence. The size of the 95% Confidence Interval would be  $2 \times \text{Accuracy}$

### 8.3 Statistical Analysis of ADA Serum Levels

ADA serum concentrations will be summarized at each time point using descriptive statistics including number of subjects, number of non-missing observations, mean, median, standard deviation, coefficient of variation (CV), minimum and maximum as appropriate. Mean and median concentration versus time plots will be generated. Data will be assessed for the following subgroups:

- Total recruited subjects;
- Subjects defined as primary sub-optimal responders at baseline, based on Investigator assessment;
- Subjects defined as secondary sub-optimal responders at baseline, based on Investigator assessment

To further characterize the relationship between ADA serum levels and treatment response, subjects will be classified as non-responders (< 50% improvement in PASI from baseline (baseline defined as addition of MTX to ADA therapy); moderate responders ( $\geq$  50% to <75% improvement in PASI from baseline) or good responders ( $\geq$  75%

---

improvement in PASI from baseline) at 8, 16 and 24 weeks. At each visit, median ADA serum levels will be evaluated by group and compared between groups.

In addition, exploratory analysis to determine possible associations between MTX dose and ADA serum levels will be carried out.

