**Figure 1: Study Design Schematic**

The study was designed to enroll 50 subjects to meet scientific objectives without enrolling an undue number of subjects in alignment with ethical considerations. Therefore, if the target number of subjects has been enrolled, there is a possibility that additional subjects in screening will not be enrolled.

---

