### **8.1.2 Planned Methods for Statistical Analysis**

Point estimates and 95% confidence intervals (CIs) will be provided for the discrete efficacy variables such as the proportion of responders to ADA + MTX. Changes from baseline (in PASI, PGA, DLQI and ADA serum levels) will be estimated using an appropriate estimation from a Mixed Model and statistical tests of change from baseline equal to zero will be carried out at the 0.05 significance level. Descriptive statistics will be provided as appropriate. These include the number of observations, mean, and standard deviation for continuous variables and counts and percentages for discrete variables. The analysis will be performed using SAS® (SAS Institute Inc., Cary, NC, USA).

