### **8.1.4 Statistical Analysis of Efficacy**

The primary and secondary efficacy analyses will be conducted on the ITT population. The primary efficacy analyses will also be conducted for the following sub-populations:

- Subjects defined as primary sub-optimal responders at baseline, based on Investigator assessment;
- Subjects defined as secondary sub-optimal responders at baseline, based on Investigator assessment.

For the primary and secondary efficacy analyses, sub-optimal responder imputation (imputing missing satisfaction data as “dissatisfied”) will be used. In the event that greater than 5% of the satisfaction data are missing, the following will be carried out to impute the missing data in sensitivity analyses:

- Last observation carried forward (LOCF): The LOCF analyses will use the completed evaluation from the previous visit within the particular period for efficacy measures assessed, to impute missing data at later visits;

Additional exploratory efficacy outcomes will be analyzed using available data at each assessment point and changes over time for PASI, PGA and DLQI scores will be estimated using a Mixed Model. Exploratory analysis to determine associations between ADA serum levels and PASI, PGA and DLQI scores will also be carried out. This could be accomplished using a regression analysis with ADA serum level and visit as explanatory variables and either PASI, PGA or DLQI as response variables and controlling for within subject measurements. To determine the form of the regression model, the exploratory analyses could be carried out using LOESS Regression or general additive models. Alternatively, subjects could be grouped according to predetermined ranges of PASI, PGA or DLQI and the analysis could concentrate on determining differences in ADA serum levels in these groups.

---

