10.2.2 Secondary Efficacy Variables

Secondary efficacy variables included:

- Based on investigator assessment, the proportion of subjects achieving a satisfactory response at scheduled visits other than Week 16
- Based on subject self-assessment, the proportion of subjects achieving a satisfactory response at scheduled visits other than Week 16
- Proportion of subjects achieving PASI 50/75/90/100 at all scheduled visits

- Change and percent change from baseline in PASI at all scheduled visits.
- Proportion of subjects achieving a clinical response defined as a PGA of "Clear" or "Minimal" at all scheduled visits
- Change and percent change from baseline in DLQI at all scheduled visits
- Based on investigator assessment, the proportion of subjects at each of the five categories of satisfaction at all scheduled visits
- Based on subject self-assessment, the proportion of subjects at each of the five categories of satisfaction at all scheduled visits
- Proportion of subjects achieving a DLQI score of 0 or 1 at all scheduled visits
- Change and percent change from baseline in BSA at all scheduled visits.
- Change from baseline in hs-CRP at all scheduled visits.

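### Protocol 8.3 relates serum ADA to PASI improvement only through three response groups; inference should use continuous percent improvement, with the groups kept as a display.

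*Protocol*

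**What the plan says.** Protocol 4.2 makes it a secondary objective to describe how changes in serum ADA correlate with changes in satisfaction, PGA, PASI and DLQI. Two protocol sections address this.

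- **Protocol 8.3.** After descriptive summaries of ADA by visit, it adds a step introduced by "To further characterize the relationship between ADA serum levels and treatment response". Three groups are formed at Weeks 8, 16 and 24, starting with "subjects will be classified as non-responders (< 50% improvement in PASI from baseline", then 50% to below 75%, then 75% or more. The analysis is: "At each visit, median ADA serum levels will be evaluated by group and compared between groups".
- **Protocol 8.1.4.** Exploratory analysis of ADA against PASI, PGA and DLQI scores is to be done; the synopsis says the same. The method is left open. It may be a regression of the score on ADA and visit, allowing for repeated measurements within a subject, with LOESS or additive models to find the form. Or: "Alternatively, subjects could be grouped according to predetermined ranges of PASI, PGA or DLQI".

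SAP 10.2.2 lists "Change and percent change from baseline in PASI at all scheduled visits", so the continuous measure will exist at every visit. SAP 3.0 leaves pharmacokinetic analysis to separate documents, which are not among those supplied.

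**The concern.** Percent improvement is continuous, and the objective speaks of correlation. Cutting at 50% and 75% treats subjects at 51% and 74% as identical and subjects at 74% and 76% as different. If the groups are then compared as unordered, their ranking is lost too.

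Protocol 8.1.4 does not clearly fill the gap. A team could follow both sections in full and never relate ADA to continuous percent improvement, because the regression is optional, models the score, and may be replaced by more grouping.

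Section 3.0 of the protocol explains that the study measures serum ADA instead of anti-drug antibodies, so this is its main view of mechanism. The planned size has fallen from about 200 to about 50. At stake is a real, moderate association that the grouped comparison fails to show and that is then described as no relationship.

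**Working it through.** **Inputs from the documents.** Planned size: "The study was designed to enroll 50 subjects to meet scientific objectives"; missing samples and dropout would lower the number per visit. Cut points are 50% and 75%. A significance level appears only for another purpose: "statistical tests of change from baseline equal to zero will be carried out at the 0.05 significance level".

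**Inputs assumed, because the documents are silent.** Two-sided 0.05 for the group comparison; one visit at a time; a bivariate normal (linear, monotone) association with correlation 0.3, 0.4 or 0.5; splits across the three groups of thirds, 50/25/25 or 75/15/10. With 50 subjects these give about 17 per group; 25, 12.5 and 12.5; and 37.5, 7.5 and 5.

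**The plan's own figure.** The plan states no power for this comparison. Its only precision figures at n=50 are the half-widths in Protocol Table 5, which reproduce: 1.96 × √(0.15 × 0.85 / 50) = 9.9%, 1.96 × √(0.30 × 0.70 / 50) = 12.7%, 1.96 × √(0.50 × 0.50 / 50) = 13.9%. They concern the satisfaction endpoint and do not bear on this point.

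**Method.** Simulate pairs of ADA and improvement for 50 subjects. Cut improvement at the quantiles that give each split. Count rejections for Spearman on the uncut scale, and for Kruskal-Wallis, Mood's median test and an ordered rank trend on the three groups. There were 3,000 runs per scenario for the first two splits and 2,000 for the third. The Monte Carlo standard error of one power figure is at most √(0.25 / 2000) = 1.1 points.

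**Check of the simulation.** Fisher's z gives Pearson power Φ(atanh(r) × √47 − 1.96). At r = 0.4 this is Φ(0.4236 × 6.856 − 1.96) = Φ(0.944) = 82.8%; the simulation gave 83.0% to 83.4%. With no association the tests rejected in about 4% to 6% of runs.

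**Results.** Power in percent, with loss against Spearman in points in brackets:

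| Split | r | Spearman | Kruskal-Wallis | Median test | Ordered trend |
|---|---|---|---|---|---|
| Thirds | 0.3 | 52.4 | 33.5 (18.9) | 24.0 (28.4) | 45.1 (7.3) |
| Thirds | 0.4 | 78.8 | 59.6 (19.2) | 43.2 (35.6) | 71.7 (7.1) |
| Thirds | 0.5 | 94.2 | 83.1 (11.1) | 65.0 (29.2) | 89.4 (4.8) |
| 50/25/25 | 0.3 | 50.6 | 31.6 (19.0) | 23.8 (26.8) | 43.2 (7.4) |
| 50/25/25 | 0.4 | 78.6 | 55.8 (22.8) | 40.5 (38.1) | 68.5 (10.1) |
| 50/25/25 | 0.5 | 94.4 | 80.1 (14.3) | 62.1 (32.3) | 88.4 (6.0) |
| 75/15/10 | 0.3 | 51 | 25 (26) | 17 (34) | see below |
| 75/15/10 | 0.4 | 79 | 41 (38) | 28 (51) | see below |
| 75/15/10 | 0.5 | 94 | 67 (27) | 46 (48) | see below |

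For the 75/15/10 split, a separate run of 2,000 put the loss for the ordered trend at 17 to 22 points; repeat runs put the upper end at up to 26. Over repeat runs the ranges are about 11 to 39 points (Kruskal-Wallis), 28 to 50 (median test; single runs 27 to 51) and 4 to 26 (ordered trend).

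**Sensitivity to shape.** Suppose instead that ADA is higher only in subjects with at least 75% improvement, by an assumed 0.8 to 1.2 standard deviations. Kruskal-Wallis then beats Spearman by about 8 to 19 points, for example 69% against 53%.

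**The case against.** The strongest reply has four parts.

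1. **The grouped comparison is an addition.** Protocol 8.3 introduces it as further characterization, and 8.1.4 commits to some exploratory analysis of ADA against PASI scores. A regression of the score over all visits with a subject effect already speaks in part to within-subject change. This stands. A reader might infer that 8.3 is the only planned link between ADA and response, and the documents do not support that. What remains is narrower: it is the only committed analysis of percent improvement, and the full-scale method in 8.1.4 is optional.
2. **No test is named.** The comparison may be meant descriptively, and much of the larger loss comes from assuming an unordered or median test. This stands too. With an ordered trend the loss is only about 5 to 10 points for the two more even splits.
3. **The cuts are not arbitrary.** PASI 50 and PASI 75 are endpoints of this trial, and the protocol's introduction cites a comparison of ADA levels between clinical responders and non-responders. That is a good reason to show the groups, though not to rest inference on them.
4. **The pharmacokinetic analysis document is unseen.** It may already fix a test or use the continuous scale, so the request has to be conditional on it.

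**Conclusion.** The point holds as a modest improvement to an exploratory secondary analysis. For a monotone linear association, three groups carry less information than continuous percent improvement, and the loss at 50 subjects can be material: at correlation 0.4, power falls from about 79% to between 41% and 60% with Kruskal-Wallis.

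A reader might take one of these ranges as a property of the plan. It is not. Correlation, group split, test and shape of association are all assumed. On a wider grid (correlation 0.2 to 0.6, splits out to 80/10/10, Pearson or Spearman as comparator) the loss runs from about 1 to 58 points, and with a threshold-shaped association the sign can reverse. Nor do the documents imply that every group will be small: under 75/15/10 the largest holds about 38.

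No primary endpoint, sample size or decision rule rests on this comparison.

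**What to change.** - **Protocol 8.3**, and the pharmacokinetic analysis document unless it already does so: base inference on continuous percent PASI improvement from baseline. Either report its Spearman correlation with serum ADA and a 95% confidence interval at Weeks 8, 16 and 24, or fit one repeated-measures model of percent improvement on ADA and visit with a subject effect. State which.
- **Three-group table of median ADA:** keep it, labelled as descriptive, with no between-group test.
- **Protocol 8.1.4:** limit the grouping alternative to display.

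The cost is wording and a few lines of programming, with no new data and no burden on subjects. One small drawback: a correlation or slope is less familiar to clinicians than PASI response groups, which is why the table stays.

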## **9.0                   Ethics**

### **9.1                   Independent Ethics Committee (IEC) or Institutional Review Board (IRB)**

Good Clinical Practice (GCP) requires that the clinical protocol, CRFs, subject dosing diary, any protocol amendments, the Investigator's Brochure, the informed consent and all other forms of subject information related to the study (e.g., advertisements used to recruit subjects) and any other necessary documents be reviewed by an IEC/IRB. The IEC/IRB will review the ethical, scientific and medical appropriateness of the study before it is conducted. IEC/IRB approval of the protocol, informed consent and subject information and/or advertising, as relevant, will be obtained prior to the authorization of drug shipment to a study site.

Any amendments to the protocol will require IEC/IRB approval prior to implementation of any changes made to the study design. The Investigator will be required to submit, maintain and archive study essential documents according to International Conference on Harmonization (ICH) GCP.

Any SAEs that meet the reporting criteria, as dictated by local regulations, will be reported to both responsible Ethics Committees and Health Canada. During the conduct of the study, the Investigator should promptly provide written reports (e.g., ICH Expedited Reports, and any additional reports required by local regulations) to the IEC/IRB of any changes that affect the conduct of the study and/or increase the risk to subjects. Written documentation of the submission to the IEC/IRB should also be provided to AbbVie.

---

**9.2                   Ethical Conduct of the Study**

The study will be conducted in accordance with the protocol, ICH guidelines, applicable regulations and guidelines governing clinical study conduct and the ethical principles that have their origin in the Declaration of Helsinki. Responsibilities of the clinical Investigator are specified in [Appendix A](#).

**9.3                   Subject Information and Consent**

The Investigator or his/her representative will explain the nature of the study to the subject, and answer all questions regarding this study. Prior to any study-related screening procedures being performed on the subject, the informed consent form will be reviewed and signed and dated by the subject, the person who administered the informed consent, and any other required signatories. A copy of the informed consent form will be given to the subject and the original will be placed in the subject's medical record. An entry must also be made in the subject's dated source documents to confirm that informed consent was obtained prior to any study-related procedures and that the subject received a signed copy. Consent must be obtained before any study-related procedures including completion of the Investigator/subject satisfaction assessment. In addition, consent must be obtained before wash-out procedures are initiated in subjects who are receiving ADA 40 mg once weekly; prior to study enrolment these subjects should be treated with ADA 40 mg eow for at least 8 weeks.

Information regarding subject reimbursement for travel expenses and information regarding provisions for treating and/or compensating subjects who are harmed as a consequence of participation in the study can be found in the informed consent form.

**10.0                  Source Documents and Case Report Form Completion****10.1                  Source Documents**

Source documents are defined as original documents, data and records. This may include hospital records, clinical and office charts, laboratory data/information, subjects' diaries or

---

evaluation checklists, completed satisfaction questionnaires, pharmacy dispensing and other records, recorded data from automated instruments, microfiches, photographic negatives, microfilm or magnetic media, and/or x-rays. Data collected during this study must be recorded on the appropriate source documents.

The Investigator(s)/institution(s) will permit study-related monitoring, audits, IEC/IRB review, and regulatory inspection(s), providing direct access to source data documents.

The following assessments will be completed by the Investigator (or qualified designee) and will be considered source documentation:

- PASI assessment
- PGA assessment
- BSA assessment
- Treatment satisfaction questionnaire

The following assessments will be completed by the subject and will be considered source documentation:

- Treatment satisfaction questionnaire
- DLQI

Once collected, these outcome assessments will be entered by AbbVie or the site into the EDC system and will be available for viewing by site personnel.

The AE eCRF data segments of: alternate etiology, severity, frequency and relationship to ADA + MTX may also be used as source documents and will require Investigator approval on the eCRF as verification of the accuracy of the information.

## **10.2 Case Report Forms**

Case report forms (CRFs) must be completed for each subject screened/enrolled in this study. These forms will be used to transmit information collected during the study to AbbVie and regulatory authorities, as applicable. The CRF data for this study are being

collected with an electronic data capture (EDC) system called RAVE® provided by the technology vendor Medidata Solutions Incorporated, NY, USA. The EDC system and the study-specific electronic case report forms (eCRFs) will comply with Title 21 CFR Part 11. The documentation related to the validation of the EDC system is available through the vendor, Medidata, while the validation of the study-specific eCRFs will be conducted by AbbVie and will be maintained in the Trial Master File at AbbVie.

The Investigator will document subject data in his/her own subject files. These subject files will serve as source data for the study. All eCRF data required by this protocol will be recorded by investigative site personnel in the EDC system. All data entered into the eCRF will be supported by source documentation.

The Investigator, or an authorized member of the Investigator's staff, will make any necessary corrections to the eCRF. All changed information, including the date and person performing the corrections, will be available via the audit trail, which is part of the EDC system. For any correction, a reason for the alteration will be provided. The eCRFs will be reviewed periodically for completeness, legibility, and acceptability by AbbVie personnel (or their representatives). AbbVie (or their representatives) will also be allowed access to all source documents pertinent to the study in order to verify eCRF entries. The principal Investigator will review the eCRFs for completeness and accuracy and provide his or her electronic signature and date to eCRFs as evidence thereof.

Medidata will provide access to the EDC system for the duration of the trial through a password-protected method of internet access. Such access will be removed from Investigator sites at the end of the site's participation in the study. Data from the EDC system will be archived on appropriate data media (CD-ROM, etc.) and provided to the Investigator at that time as a durable record of the site's eCRF data. It will be possible for the Investigator to make paper printouts from that media.

---

## **11.0                   Data Quality Assurance**

Prior to the initiation of the study, an Investigator's meeting and/or a study initiation visit will be held with the Investigators, their sub-Investigators and study coordinator(s) and AbbVie personnel and/or their designee. This meeting will include a detailed discussion of the protocol, performance of study procedures, completion of the eCRFs, subject questionnaires, subject dosing diary cards, and specimen collection methods.

The CRA will monitor each site throughout the study and source document verification will be performed.

All data entered in the database will be verified at AbbVie. Any discrepancies will be reviewed. The data will be reviewed and computer logic and manual checks will be created to identify items such as inconsistent study dates. A manual review of selected line listings will also be performed at the end of the study. Queries will be generated in the EDC system. Any necessary corrections will be made to the eCRF and documented via addenda or audit trail. The data from the central laboratory analyses will be electronically transferred from the central laboratory to the study database. A final review of all laboratory results will be conducted by a physician and clinical review team at AbbVie.

